2. BACKGROUND AND RATIONALE

A. Significance

A.1. Postoperative delirium is a serious, unmet public health need:

Delirium costs an estimated \$38–\$164 billion annually in the US and causes untold stress on patients, their families, and caregivers. It predicts greater risk of institutionalization, Alzheimer's disease and related dementias (ADRD), and death.³⁻⁵ A third of all older adults have delirium during medical hospitalization. After cardiac surgery, 25–50% develop delirium.⁶ More than 75% of critically ill adults and up to 85% of palliative care patients at the end of life develop delirium.⁷ Despite its tremendous public health significance, most delirium is not preventable with current interventions,⁸ and no intervention decisively improves delirium or its outcomes, including ADRD.⁹ **There is a dire need for efficacious, well tolerated interventions to prevent and treat delirium.**

A.2. Delirium after heart surgery is especially important:

Cardiac surgery is plagued with delirium: rigorous studies report 25–50% incidence.⁶ Post-cardiotomy delirium prevention has also often met with a sense of nihilism¹⁰ due to unique challenges relative to other surgical cohorts,¹¹ only underscoring the need for efficacious delirium therapeutics in this population. **Post-cardiotomy delirium is associated with nearly 3x higher mortality, 6x higher risk of 24h+** mechanical ventilation, and longer ICU and hospital duration.¹²

A.3. Sleep/wake disturbance (SWD) confer vulnerability to delirium^{9,13-15}:

SWD is a core feature of delirium,¹⁶⁻²⁰ with research diagnostic criteria for delirium including SWD as one of delirium's three core domains.^{20,21} Although whether SWD directly cause delirium has yet to be established,^{22,23} there is strong evidence for the physiological link between SWD and delirium. Sleep is governed by the diencephalon (*i.e.*, hypothalamus and thalamus).²⁴ The anterior hypothalamus contains the sleep/wake "switch," which coordinates transitions between sleep and wake via dense reciprocal connections with all major sleep/wake centers in the brain.²⁵ The thalamus controls slow waves,²⁶ sleep spindles (linked with attentional disorders),²⁷ and sensory gating.²⁸ Each of these sleep/wake processes regulated by the diencephalon is disrupted in delirium,²⁹⁻³² strongly suggesting that maintaining or restoring sleep/wake integrity could combat delirium. Given that SWD are modifiable, they are an obvious and promising target for innovative pharmacological trials to prevent delirium.^{9,13-15}

A.4. Prior "sleep" trials for delirium are methodologically limited³³:

Most prior trials have studied *circadian* interventions and conflate the two related but dissociable processes of sleep/wake—process S (*sleep* propensity) and process C (endogenous *circadian* rhythm).³⁴ Melatonin/melatonin agonists influence circadian rhythms but have very limited effects on sleep quality.³⁵ Most prior circadian trials, which have yielded negative results,³⁶⁻⁴⁷ have used *circadian* interventions with the goal of improving *sleep*, rather than studying them according to circadian principles, such as evaluating premorbid circadian phase to inform timing or evaluating circadian rhythmicity.⁴⁸ Sleep studies need to consider the specific effects of an intervention on sleep architecture (*e.g.*, REM sleep, N2 transients, N3), which is different from circadian studies that should evaluate effects on circadian rhythm (*e.g.*, 24-hr amplitude, dim-light melatonin onset).⁴⁹

A.5. Orexin stabilizes sleep and wake states:

Orexin, also called hypocretin, is secreted by the tuberal hypothalamus and stabilizes sleep and wake states. Central orexin deficiency is the underlying cause of type 1 narcolepsy, which presents with excessive daytime sleepiness accompanied by either an irrepressible need to sleep or frank lapses into sleep.⁵⁰ The densest orexin projections are to the noradrenergic locus coeruleus with other projections to the cholinergic basal forebrain and serotonergic raphe nuclei.⁵⁰ **Orexin receptor (OX1R/OX2R) antagonism inhibits noradrenergic activity, thereby facilitating sleep onset.**⁵¹ In humans, orexin antagonism increases total sleep time, reduces sleep latency, and reduces wake after sleep onset.⁵²

A.6. Application of dual orexin receptor antagonists (DORAs) to neurodegenerative disorders:

Many reasons encourage studying DORAs in relation to delirium. DORAs (1) are efficacious in older adults; ^{52,53} (2) have good tolerability in older adults, including at the highest approved doses; ^{52,53} (3) do not suppress N2 transients, N3 sleep, or REM sleep; ⁵⁴ (4) lack GABA-ergic activity; ⁵⁵ (5) lack clinically significant anticholinergic effects; ⁵⁶⁻⁵⁸ (6) do not prolong the QTc to a clinically relevant degree; ⁵⁶⁻⁵⁸; (7) have very limited abuse liability; ⁵⁹ (8) do not cause rebound insomnia or withdrawal; ⁶⁰ (9) improve total sleep time in obstructive sleep apnea; ⁶⁰ (10) do not worsen obstructive sleep apnea at therapeutic doses; ⁶¹ (11) reduce stress-induced insomnia ⁶² and exert anxiolytic effects ⁶³ in rodent models; and (12) appear to improve CSF clearance of Alzheimer disease biomarkers even after a single nightly dose. ⁶⁴ Their effects on postural stability ⁶⁵ and reaction time ⁶⁶ are limited, and less than those of GABA-ergic agents like benzodiazepines. The three FDA-approved DORAs are similar pharmacologically; however, daridorexant has the shortest half-life and negligible next-morning effects in clinical trials (Table 1). ^{52,67,68} Given that cognitive performance is worst in the morning, especially attention ⁶⁹ (n.b., inattention is delirium's hallmark feature), and that delirium assessments often occur in the morning, the ideal DORA for delirium prevention should have negligible morning cognitive effects. Thus, daridorexant is the most promising DORA for delirium prevention.

Table 1 - Comparison of DORAs approved by the US FDA for insomnia						
	Daridorexant	Suvorexant	Lemborexant			
OX1R binding affinity (Ki)	0.47 nM	0.55 nM	6.1 nM			
OX2R binding affinity (Ki)	0.93 nM	0.35 nM	2.6 nM			
Major metabolite	None	None	M10			
Effects on QTc	Not clinically relevant	Not clinically relevant	Not clinically			
			relevant			
Mean T _{max}	1-2 hours	2 hours	1-3 hours			
Volume of distribution	31 L	49 L	1970 L			
Terminal t _{1/2}	8 hours	12 hours	17 hours			
Metabolism	CYP3A4 (89%)	CYP3A > CYP2C19	CYP3A4 > CYP3A5			
Severe liver impairment	"Not recommended"	"Not recommended"	"Not recommended"			
Severe renal impairment	50% higher C _{max}	No dose adjustment	50% higher C _{max}			

A.7. A new program of sleep-delirium trials:

This proposed trial is the first in an anticipated research program that aims to combat delirium with sleep interventions. This project builds on the PI's K23 work investigating SWD in relation to delirium and will serve as a transition into translational research to develop sleep-focused delirium therapeutics.

A.8. Whether sleep-focused interventions combat delirium, thus improving long-term cognitive outcomes, is unproven:

SWD are also closely associated with the permanent, progressive conditions of AD and CVD, which cause dementia, and considered a potential mechanism causing or accelerating these conditions, ^{14,70-73} perhaps by way of disrupted glymphatic clearance. ⁷⁴ If (a) delirium mediates the relationship between SWD and AD/CVD and (b) preserving healthy sleep/wake prevents delirium, ^{64,75-77} then preventing delirium could prevent subsequent AD/CVD. ⁷³ What the field needs are conclusive data linking discrete sleep/wake interventions with the prevention of delirium and its dire cognitive and functional outcomes, including ADRD. This project is aligned with the ADRD Milestones as it investigates targets of delirium vulnerability along with longer-term outcomes ⁹ by examining the mechanisms that link delirium physiology with its sequelae. ⁷⁸

A.9. Summary of significance:

Although delirium is an acute event, it often has permanent effects on patients' cognition and function. To date, no medication is FDA-approved to prevent or treat delirium, along with its terrible costs to patients, their families, and health systems.

B. Innovation

B.1. The orexin system invites delirium-related investigation:

Orexin is a promising alternative target to GABA for sleep pharmacology, especially in older adults. Early evidence suggests that DORAs may have a role in relation to delirium. $^{75,76,79-83}$ Both published RCTs of the DORA suvorexant to prevent delirium were positive but have methodological limitations, including that neither was double-blind. The first, from 2017, randomized 72 ICU and medical unit patients (mean age 78) to suvorexant or placebo in a "rater blind" manner and found a lower delirium incidence with suvorexant: 0 (0%) vs 6 (17%), p = 0.025. The second, from 2018, randomized ICU patients to placebo or standard care and found a longer time to delirium with suvorexant (6.3d vs 5.7d, log–rank test p < 0.05); ⁸⁴ however, 80% of comparison arm subjects arm received as-needed trazodone 25 mg qhs, confounding

Version date: 2/3/2025

clinical interpretation. Critical readers are skeptical about these data, as with any delirium study that finds a 0% delirium incidence in any study arm. Further, rigorous delirium trials have often failed to replicate early delirium studies: for instance, despite a promising 2014 ramelteon trial⁸⁵ (n.b., from the authors of the 2017 suvorexant trial above) have not held up, as shown in a 2023 meta-analysis.86 Moreover, compelling data will be needed to overcome a general apprehension re the use of sleep aids in older adults and the prevailing convention that they be used only as a "last resort."87 The field awaits the first double-blind RCT to prevent postop delirium and the first delirium prevention RCT of daridorexant.

B.2. This study employs methodologically rigorous trial design using a true sleep aid:

As above, most prior "sleep" studies for delirium have investigated circadian interventions rather than interventions that improve sleep quality. This study aims to overcome the limitations of these prior trials by using an agent demonstrated to improve sleep quality and shorten wake bout duration using rigorous trial design (Error! Reference source not found.).

Table 2 - Considerations in sleep-delirium trials

Methodological consideration	Limitations of prior trials
The agent should enhance sleep.	Agents that entrain circadian phase.
The sleep aid should be taken each night before delirium assessments.	Several trials with non-nightly dosing. 39,40,42,46,47
Sleep should be evaluated across subjects as a measure of primary effect	Most have neglected to assess sleep. ³⁹⁻ 41,43,44,47
Baseline sleep health should be evaluated.	Very rare in prior studies (e.g. ⁴⁶).
Accounting for in-hospital sleep disruptions.	Done in only three (i.e., 36,37,45).
Measure of ADRD biomarkers	Not done previously.

B.3. This project represents a transition from observational to interventional research for the PI:

This trial represents the first of an anticipated program of sleep-focused clinical trials to prevent as well as treat delirium. The delirium field is replete with observational research in delirium predictors and outcomes. 88,89 However, there is far less translational inquiry, and precious little evidence of efficacious interventions. 90 A new generation of double-blind, placebo-controlled trials is urgently needed in the delirium field.

B.4. Summary of innovation:

This daridorexant trial studies a highly promising, novel intervention to prevent postop delirium in older adults, a condition for which there is no approved medication and little translational inquiry. Preventing delirium would improve postop recovery and well-being and might even reduce the neuropathological progression of AD. This is the first trial to study daridorexant to prevent delirium in any context. Establishing that daridorexant prevents delirium could have immediate, transformative value for clinical practice.

3. ADMINISTRATIVE ORGANIZATION

This single-site trial represents a collaboration among the Department of Psychiatry, Department of Anesthesiology, and the Department of Surgery, Division of Cardiac Surgery, Randomization with a block size of six and drug dispensing will occur through Investigational Drug Services (IDS) at Strong Memorial Hospital (SMH). Prospective subjects may be identified in the hospital while awaiting surgery, at the time of outpatient evaluation by a cardiac surgeon, or in conjunction with anesthesiology during pre-surgical history and physical, typically performed at the Center for Perioperative Medicine.

Version date: 2/3/2025

4. STUDY DESIGN

This double-blind, parallel-group trial will randomize patients having cardiac surgery—either surgical aortic valve replacement (SAVR) or coronary artery bypass graft (CABG) surgery—to oral daridorexant 50 mg or identical-appearing placebo. The primary outcomes are feasibility and safety. Study subjects will provide written informed consent after receiving a complete description of the study. See Figure 1 below for a timeline of study assessments (not to scale).

[figure not shown]

Figure 1 – Timeline of Study Assessments

Abbreviations: 3D-CAM, 3-minute Diagnostic interview for the Confusion Assessment Method; CAGE-AID, CAGE [an acronym for "Cut down, Annoyed, Guilty, Eye-opener"] Adapted to Include Drugs; **POD**, postoperative day; **PON**, postoperative night; **TICS**, Telephone Interview for Cognitive Status *25 mg for subjects on a moderate 3A4 inhibitor (see 4.2 STUDY INTERVENTION below for details)

4.1 SUBJECT POPULATION

We will enroll 16 persons scheduled to have SAVR or CABG at SMH, with the goal of having 12 subjects complete the protocol.

Choice of study population:

We propose a cardiac surgery cohort for several reasons. (1) Surgery provides a convenient model for understanding delirium pathophysiology and interventions as it allows for describing the sample at baseline and prospectively evaluating a cohort at elevated risk of delirium. (2) Cardiac surgery is associated with a 25–50% delirium incidence⁶, due in large part to the older mean age of this population. As noted above, we have found 30% delirium incidence after SAVR at our institution. (3) We select a cardiac surgery cohort over a hip repair cohort as the pain associated with hip pathology and the postop surgical site affects sleep positions before and after surgery, which contributes to SWD, thereby introducing a potential confound.

The subjects in this trial do not qualify as vulnerable populations.

4.2 STUDY INTERVENTION

We will administer enteral daridorexant 50 mg each evening before bedtime, from 8 to 10 PM. Per the package insert,⁵⁸ subjects taking a moderate inhibitor of CYP 3A4 (per searchable FDA site⁹²) will receive a reduced dose of 25 mg. Moderate inhibitors of 3A4 include: aprepitant, ciprofloxacin, conivaptan, crizotinib, diltiazem, dronedarone, erythromycin, fluconazole, grapefruit juice, imatinib, isavuconazole, verapamil. Of these, those most likely to be present are the antibacterials ciprofloxacin or erythromycin or the calcium channel blockers diltiazem or verapamil.

Choice of agent and dose:

DORAs represent a promising class of agents for delirium studies. In a phase 3 trial vs placebo, daridorexant 50 mg reduced wake after sleep onset (WASO) and latency to persistent sleep (LPS) on polysomnography (-22.8 min [95% CI -28.0 to -17.6); -11.4 min [-16.0 to -6.7], respectively), as well as

improved self-reported total sleep time (TST) (22.1 min [14.4 to 29.7]) and Insomnia Daytime Symptoms and Impacts Questionnaire sleepiness scores (-1.8 [-2.5 to -1.0).⁵² Lower doses (10 & 25 mg) had less effect on sleep outcomes, with some not reaching statistical significance.⁵² Although the 50-mg dose had greater efficacy, its AEs were nearly identical to that of lower doses (**Table 3**, see below⁵²). Daridorexant improved WASO, LPS, and subjective TST comparably in older (≥ 65 yr) and younger adults (< 65 yr), with nearly identical rates of AE.⁵³ Another concern for most sleep aids is risk of falls; however, among older adults, **falls were numerically** *less likely* with either **25 or 50 mg daridorexant than with placebo (1/119 [0.8%], 1/119 [0.8%], 4/122 [3.3%], respectively).⁵³ Daridorexant improves not only sleep but also next-day functioning, as one would hope for an ideal sleep aid. Given that central orexin deficiency is the putative cause of type 1 narcolepsy, core features of narcolepsy are theoretically possible with DORAs. Nevertheless, among older adults, these were extremely** rare: 1/121 taking 25 mg daridorexant reported excessive daytime sleepiness, and 1/119 (1%) on daridorexant 50 mg reported sleep paralysis.⁵³ **We propose using 50 mg rather than 25 mg to maximize the chances of clinical effect, as this higher dose does not appear to increase the risk of AEs.**

Table 3 - Adverse events (AEs) & serious AEs (SAEs) with daridorexant (DAR) & placebo⁵²

	Placebo	Placebo	DAR 50	DAR 25	DAR 25	DAR 10
	Study 1	Study 2	mg	mg	mg	mg
	n=309	n=306	Study 1	Study 2	Study 2	Study 2
			n=310	n=308	n=308	n=306
Any AE	105	100	116	117	121	117
	(34%)	(33%)	(38%)	(38%)	(39%)	(38%)
Any SAE	7 (2%)	7 (2%)	3 (1%)	2 (1%)	3 (1%)	3 (1%)
Nasopharyngitis	20 (6%)	16 (5%)	20 (6%)	21 (7%)	13 (4%)	16 (5%)
Headache	12 (4%)	11 (4%)	19 (6%)	16 (5%)	15 (5%)	12 (4%)
Somnolence	6 (2%)	4 (1%)	5 (2%)	11 (4%)	10 (3%)	6 (2%)

Choice of dosing days/times:

We will give 50 mg daridorexant (25 mg to those on moderate 3A4 inhibitor, as above) or placebo 8-10 PM on the first 3 postop nights and evaluate delirium on each of the days following administration—*i.e.*, POD 1–3. We give study agent the night prior to each day's assessment because **the prior night's sleep directly impacts cognition the next day**. Sleep restriction causes neurocognitive impairment the following day with the most pronounced effects in sustained attention (vigilance). We choose 8-10 PM because daridorexant's T_{max} is 1–2 hr. This (1) allows time for its soporific effect and (2) is early enough to mitigate next-morning sedation). S2,67,68 For any subject still intubated during the 8-10 PM window, we will allow for administration up to midnight in the event that they are extubated prior to midnight. This is to maximize the likelihood of administration on the first postoperative night.

Justification and safety information if FDA approved drugs will be administered for non-FDA approved indications or if doses or routes of administration or subject populations are changed:

On September 18, 2024, we received a determination from the US FDA that our proposed trial "meets all meets all of the requirements for exemption from the IND regulations and, therefore, an IND is not required to conduct [this] investigation." See attached document, "FDA exemption determination (24-09-18)."

Medication and matching placebo will be stored by IDS, who will be responsible for randomization subjects to study arms, keeping records on medication storage, and ensuring timely dispensing.

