5. INCLUSION

Inclusion criteria:

 \geq 60 yrs; having cardiac surgery at Strong Memorial Hospital; can provide consent; able to speak, read, and write English (as the instruments, including semi-structured interviews, used in this protocol have been validated in English); family member or close friend for collateral.

Exclusion criteria:

Exclusion criteria with rationales are described in **Table 4**. Subjects will be screened in person or by phone for eligibility.

Table 4 - Exclusion criteria with explanation				
Exclusion criteria	Definition (rationale)			
Prior cardiotomy	Per self-report or chart (sequelae of prior surgery)			
Infectious endocarditis	Per chart (potential septic emboli)			
Emergency surgery	Per chart (baseline eval impossible)			
Delirium at baseline	Positive 3D-CAM (limit to incident delirium)			
Auditory/visual impairment prevents study procedures	Per self-report or demonstrated inability during baseline visit (inability to participate)			
Alcohol/substance misuse	CAGE-AID score of 2 or greater (exclude cognitive effects of substances)			
Psychotic disorder	Per self-report or chart (can confound delirium assessment)			
Dementia-level deficits	Per self-report, chart, or TICS < 27 (exclude effects of dementia on delirium assessments)			
Use of a sleep aid	Any prescribed sleep aid being taken at least every other night (potential confound)			
Use of a strong 3A4 inhibitor (per FDA website ⁹²)	Ceritinib, clarithromycin, cobicistat, idelalisib, itraconazole, ketoconazole, nefazodone, nelfinavir, posaconazole, ritonavir, telithromycin, voriconazole (increases drug exposure)			
Intolerance to daridorexant	Per self-report or chart (safety)			
Severe kidney or liver impairment	Child-Pugh score ≥ 7, Cockcroft-Gault < 30 mL/min, or current dialysis (safety)			
Narcolepsy	Per self-report or chart (daridorexant is contraindicated in narcolepsy)			
Prior suicide attempt	Per self-report or chart (package insert indicates a risk of worsening depression or suicidality)			
Suicidal ideation at baseline assessment	Per self-report (package insert indicates a risk of worsening depression or suicidality)			
Any condition that in th study	e opinion of the PI compromises patient safety or data quality if enrolled in the			

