8. STUDY PROCEDURES

See Table 5 below for the Schedule of Activities

Table 5 - Schedule of activities

Assessment	Screenin	Baseline	PON 1-3	POD 1-3	POD 3-7
	g	(1 hr)	(with	(15 min)	(15 min)
	(15 min)		bedtime		
			meds)		
Verbal consent	X				
CAGE-AID	X				
Written consent		X			
Demographics		X			
CCI		X			
Medication list		X			
Cognition/function					
TICS	X				
MoCA		Full, v8.1			
Lawton		X			
CDR		X			
WTAR		X			
Delirium					
3D-CAM	X			X	Χ [†]
DRS-R98				X	X [†]
Mental health					
PHQ-9		X			
GAD-7		X			
Sleep-related					
PSQI		X			
ESS		X			
RCSQ				X	X [†]
Medication administration			X		
AEs/SAEs					
Questionnaire		X		X	
Chart review*				X	X [†]
Subject to guess whether they received				POD 3	
daridorexant or placebo	 				

Abbreviations: **3D-CAM**, 3-Minute Diagnostic Interview for Confusion Assessment Method; **CAGE-AID**, CAGE [acronym for "Cut-down, Annoyed, Guilt, Eye-opener"] adapted to include drugs; **CCI**, Charlson comorbidity index; **CDR**, Clinical Dementia Rating; **DISH**, Depression Interview and Structured Hamilton; **DRS-R98**, Delirium Rating Scale, Revised 98; **ESS**, Epworth Sleepiness Scale; **GAD-7**, 7-item Generalized Anxiety Disorder scale; **Lawton**, Lawton Instrumental Activities of Daily Living; **MoCA**, Montreal Cognitive Assessment; **PHQ-9**, 9-item Patient Health Questionnaire; **POD**, postoperative day; **PON**, postoperative night (*i.e*, the night of POD 0 [the day of surgery] is defined as PON 1); **PSQI**, Pittsburgh Sleep Quality Index; **RCSQ**, Richards-Campbell Sleep Questionnaire; **TICS**, Telephone Interview for Cognitive Status; **WTAR**, Wechsler Test of Adult Reading

Screening procedures:

As indicated under **7. CONSENT PROCESS** above, consent will involve two steps—a verbal consent for study eligibility screening and, subsequently, signed consent. When obtaining verbal consent, we will

^{*}For evidence of adverse events, documentation of delirium, potential sleep confounds

[†]Daily assessments for delirium and sleep will continue if the subject is delirious on POD 3, until delirium resolves.

Version date: 2/3/2025

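### The daridorexant dose depends on CYP3A4 inhibitor use on the dosing nights, but medications are scheduled to be recorded only before surgery, and no rule covers a strong inhibitor started after entry

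*Protocol*

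**What the plan says.** Section 4.2 sets a 50 mg evening dose, reduced to 25 mg for "subjects taking a moderate inhibitor of CYP 3A4". It lists the moderate inhibitors and singles out ciprofloxacin, erythromycin, diltiazem and verapamil as the likeliest to be met. Under the choice of dosing days it ties the rule to the nights of treatment: "25 mg to those on moderate 3A4 inhibitor, as above) or placebo 8-10 PM on the first 3 postop nights". The footnote to Figure 1 in section 4 repeats the rule ("25 mg for subjects on a moderate 3A4 inhibitor") and sends the reader back to section 4.2 for details.

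Table 4 in section 5 excludes "Use of a strong 3A4 inhibitor" at entry and gives increased exposure as the reason. Table 1 puts the CYP3A4 share of daridorexant metabolism at 89%.

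In Table 5 (section 8), the row "Medication list" is marked once, under Baseline. The PON 1-3 column holds only administration of study drug. The abbreviations state that "the night of POD 0 [the day of surgery] is defined as PON 1". Chart review is marked from POD 1, and its footnote gives its purpose: "For evidence of adverse events, documentation of delirium, potential sleep confounds".

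Section 4.2 makes the Investigational Drug Service (IDS) responsible for storage, randomization, "keeping records on medication storage, and ensuring timely dispensing". Section 9 has the treating team order study drug for the three nights, after education on the trial, its methods, the need to order and the duty to report adverse events.

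**The concern.** The dose rule depends on what the subject is taking on each dosing night. The only scheduled record of what the subject takes is made before surgery. The drugs that section 4.2 expects to meet are two antibacterials and two calcium channel blockers, and it is reasonable to infer that these could be started around cardiac surgery. A preoperative list cannot show such a start.

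The stake is avoidable extra exposure in patients aged 60 or over who have just had cardiac surgery, in a trial that names safety as a primary outcome. The effect on interpretation is smaller. Section 9 records contributing factors for each adverse event and has medical records reviewed, so an inhibitor could usually be found after an event. That review follows the dose and does not prevent it.

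**Working it through.** The plan gives no figure to reproduce, so the check sets the provisions side by side and asks, for each dose, whether any scheduled step would reveal an inhibitor.

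1. **Does the rule apply at dosing or only at Baseline?** At dosing. Section 4.2 links the 25 mg dose to subjects on an inhibitor on the first three postoperative nights, and nothing limits it to Baseline status.

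2. **What is scheduled before each dose?**
   - First dose (PON 1, the evening of surgery): the last scheduled look at medications is the Baseline list. The first postoperative chart review is on POD 1, after this dose.
   - Second and third doses (PON 2 and PON 3): the POD 1 and POD 2 chart reviews may precede them, but their stated purposes do not include inhibitor use. A new inhibitor might be noticed incidentally.

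3. **Is anyone else given the check?** IDS's listed duties do not include an interaction check. The treating team's listed duties are to order study drug and report adverse events. The steps to minimize risk in section 9 rely on the entry exclusions, daily interview and record review. No section names a person to confirm inhibitor status before a dose.

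4. **How many doses does this touch?**
   - Doses in 12 completers: 12 × 3 = 36. If all 16 enrolled subjects are dosed: 16 × 3 = 48.
   - Doses given before any scheduled postoperative study review: one per subject, so 12 of 36 (or 16 of 48). This counts all first doses, not doses given with an inhibitor.
   - Size of the error where it occurs: 50 / 25 = 2 times the specified dose, on 1 to 3 nights.

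5. **What happens if a strong inhibitor is started after entry?** Table 4 operates at entry, so a later start does not breach it. Section 4.2 has one reduction, for moderate inhibitors, and otherwise specifies 50 mg. No section gives a hold or another dose.

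**The case against.** The strongest reply is that the dose rule is correct as written. It already refers to status at dosing, so 50 mg given with a known moderate inhibitor would be a deviation. Who looks at the orders, and where it is recorded, may sit in an order set or pharmacy procedure that is not shown. The ordering clinicians are responsible for the patient's other drugs and are taught the study methods, an investigational pharmacy dispenses, and the PI monitors safety. Much of this stands: these people may well catch a new start. It does not close the gap, because the written methods contain no check to teach, and the one scheduled medication record cannot see a start after Baseline.

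The length of the gap is also open. Section 8 dates screening at usually one to two weeks before surgery but does not date the Baseline list, and section 3 allows subjects to be identified in hospital while awaiting surgery. For some subjects the list may be close to dosing, although still before surgery.

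A reader might infer three stronger points that the documents do not support:

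- **That the protocol obliges 50 mg alongside a strong inhibitor**, because section 8 leaves current therapy unchanged and section 13 removes subjects only for serious adverse events. The first protects the patient's own treatment and the second governs removal from the study. Withholding one study dose is compatible with both. The protocol is silent; it does not mandate the dose.
- **That Aim 2 would count a wrong-strength dose as a success.** Section 1 words that aim as delivery according to the proposed methods, and 50 mg where section 4.2 calls for 25 mg is not that.
- **That a probability of misdosing can be quoted.** It would need a start rate and a miss rate, and the documents give neither.

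**Conclusion.** The concern holds as a gap in ascertainment. Section 4.2 makes the dose depend on postoperative inhibitor use, Table 5 records medications only before surgery, and postoperative chart review has other purposes and starts after the first dose. The scheduled procedures can therefore miss a moderate inhibitor started around surgery, with 50 mg given where 25 mg is specified. For a strong inhibitor started after entry, the default is 50 mg with no hold rule, which sits poorly with the exposure reason for excluding such use at entry.

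The consequence per case is twice the specified dose on up to three nights for a moderate inhibitor. For a strong inhibitor it cannot be sized, because the documents give no exposure ratio. Frequency cannot be estimated either. The conclusion rests on two assumptions: that drugs on these lists are sometimes started around surgery, and that no procedure outside the protocol already requires the check. Figure 1 is not shown, but its footnote points back to section 4.2. This is a worthwhile, inexpensive safety improvement and does not undermine the feasibility aims.

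**What to change.** Add to the PON 1-3 column of Table 5 a check of active orders before each dose, made by a named existing role against the moderate-inhibitor list in section 4.2 and the strong-inhibitor list in Table 4, with the result recorded. Add two rules to section 4.2:

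- With a moderate inhibitor present, IDS dispenses 25 mg or matching placebo, so the blind is kept.
- With a strong inhibitor present, that night's study drug is held, the subject stays in the study, and the event is recorded as a protocol-specified hold.

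The provisions on current therapy (section 8) and on removal (section 13) need no change.

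The cost is a short amendment and a few minutes per dosing evening: 36 checks for 12 completers, at most 48 if all 16 are dosed. No extra staff are needed. The downside is that IDS may occasionally have to change strength the same evening, within the 8-10 PM window.
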